Statistical Methods: Assuming a treatment difference of 1.1 points with a standard deviation of 1.7 in the mean change from baseline in binge eating days per week at Weeks 7-8 in either centanafadine dose group (high dose centanafadine or low dose centanafadine) compared to the placebo group (effect size = 0.65), a sample size of 114 evaluable subjects (38 in each treatment arm) will yield at least 80% power to detect the treatment effects at a 2-tailed significance level of 0.05. Approximately 126 subjects will be randomized (42 in each treatment arm) to ensure 114 evaluable subjects in the study. The primary efficacy analysis will be performed by fitting a mixed-effect model repeated measures (MMRM) analysis with an unstructured variance covariance structure, in which change from baseline in binge eating days per week at the scheduled visits will be the dependent variable based on the observed cases (OC) data set. The model will

include fixed effect terms for treatment, trial center, visit week, and an interaction term of treatment by visit week. The model will also include the interaction term of baseline values of binge eating days per week by visit week as covariates. The primary comparison between centanafadine groups and the placebo group at Weeks 7-8 will be estimated as the difference between Least Squares means utilizing the computing software SAS procedure PROC MIXED. If there is a convergence problem with the unstructured variance covariance matrix of the MMRM model, the following structures other than unstructured will be used in order of 1) heterogeneous toeplitz, 2) heterogeneous autoregressive of order 1, and 3) heterogeneous compound symmetry and the first (co)variance structure converging to the best fit will be used as the primary analysis. If a structured covariance has to be used, the "sandwich" estimator of the standard error of the fixed effects parameters will be used in order to deal with possible model misspecification of the covariance matrix.

[figure not shown]
Trial Duration:

The anticipated duration for each participant to complete the trial is up to 13 weeks, which will include the following periods:

- Screening period: up to 4 weeks (28 days)
- Double-blind treatment period: 8 weeks
- Follow-up period: 7 (+ 2) days

Overall, the trial duration from signing of the first informed consent form to the final subject assessment is expected to be approximately 10 months.

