5.4 Screen Failures

A screen failure is a subject from whom informed consent is obtained and is documented in writing (ie, subject signs an ICF), but who is not randomized or assigned trial treatment. All AEs must be reported after subject informed consent has been obtained, including screening failures due to AEs, irrespectively of IMP administration.

If the subject meets the definition of a screen failure in this trial, the following information will be recorded in the eCRF:

- Date of informed consent
- Visit date (screening visit)
- Demographics (collection date, birth date, sex at birth, race, ethnicity)
- Result of eligibility assessment
- Screen failure date
- Reason for screen failure

In the event that a subject cannot be randomized prior to the expiration of the 28-day screening period, additional extension of screening may be requested and discussed with the medical monitor. Any extension should be requested prior to the expiration of the screening period, as applicable. If no extension is granted, and the subject meets criteria for rescreening after the screening period has expired, a new ICF must be signed, a new screening number assigned, and all screening procedures repeated.

In the case that subjects sign a consent form but have not started on treatment, subjects are permitted to be rescreened if exclusion criteria have changed and following consultation with the Medical Monitor. In the event that the subject is rescreened for trial participation, including after the 28-day screening period expires, a new consent form must be signed, a new screening number assigned, and all screening procedures repeated.

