8.7.4 Electrocardiogram

Electrocardiograms will be performed at the time points described in the schedule of assessments (Table 1.3-1). ECGs scheduled for the same visit as blood samples should be completed before blood is drawn. The 12-lead ECGs will be performed in the supine position. 12-lead ECGs conducted at screening will be performed in triplicate, taken approximately 5 minutes apart. Based on the QTcF correction, a subject will be excluded if the correction equals or exceeds 450 msec for males and 470 msec for females for 2 or more of the 3 ECGs conducted. If only 1 ECG has a corrected QTcF of equal to or greater than 450 msec for males or 470 msec for females and it is not reproduced at either of the other 2 assessments, the subject meets the inclusion criteria. Only if results are exclusionary at screening will a repeat ECG be performed prior to the baseline visit; the results must be available and inclusionary prior to randomization. All subsequent ECG assessments require a single ECG recording.

Any abnormalities considered by the investigator to be clinically significant are to be recorded as AEs on the AE eCRF.

A central ECG service will be utilized for reading all ECGs in order to standardize interpretations for the safety analysis. In addition, ECG results will be evaluated at the trial site to monitor safety during the trial.

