3.1 Type/Design of Trial

This is a phase 2, multicenter, randomized, double-blind, placebo-controlled trial to assess the efficacy, safety, and tolerability of centanafadine SR tablets for the treatment of adult subjects with BED. Subjects with a primary clinical diagnosis of moderate to severe BED based on the Diagnostic and Statistical Manual of Mental Disorders, Fifth Edition (DSM-5) diagnosis criteria and confirmed by the Structured Clinical Interview for DSM-5 Disorders, Clinical Trials Version (SCID-5-CT) is eligible for enrollment. The trial consists of a screening period of up to 28 days that includes completion of a binge eating diary for at least 14 days (that shows at least 3 binge eating days in each week during the previous 14 days of a subject's screening period as reviewed at baseline [minimum screening period is 2 weeks]), a baseline visit, an 8-week (56-day) double-blind treatment period, and a 7-day safety follow-up period. All baseline assessments are conducted prior to first dose of investigational medicinal product (IMP). The design scheme is summarized in Figure 3.1-1.

Eligible subjects are randomized 1:1:1 at baseline to receive 1 of 2 doses of centanafadine SR or placebo daily for 8 weeks. All subjects who terminate early are required to participate in a 7-day safety follow-up period, which consists of telephone contact 7 (+ 2) days after the last dose of IMP. For subjects who early terminate, they are instructed to refrain from using prohibited concomitant medications, including BED treatments, until after the safety follow-up visit.

N = number of subjects; R = randomization; T = telephone visit.

Figure 3.1-1 Trial Design Schematic

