9.6 Electrocardiogram Data

For the analysis of QT and QTc, data from three consecutive complexes (representing three consecutive heart beats) will be measured to determine average values. The following QT corrections will be used for reporting purposes:

- QTcF is the length of the QT interval corrected for heart rate by the Fridericia formula: QTcF=QT/(RR)^{0.33}
- QTcN is the length of the QT interval corrected for heart rate by the FDA Neuropharm Division formula: QTcN=QT/(RR)^{0.37}

Potentially clinically relevant changes in the 12-lead ECG identified for the safety analysis set will be listed and summarized by treatment group. Criteria for identifying ECG measurements of potential clinical relevance are provided in Appendix 3.

Categorical changes in ECG parameters will be summarized by treatment group based on the following criteria in Table 9.6-1.

Table 9.6-1	Categorical Change Criteria in QT/QTc Parameters		
Classification	Category	Criteria	
QT	New Onset (> 450 msec)	New onset (>450 msec) in QT means a subject who attains a value > 450 msec during treatment period but not at baseline.	
QTc *	New Onset (> 450 msec)	New onset (> 450 msec) in QTc means a subject who attains a value > 450 msec during treatment period but not at baseline.	
	New Onset (> 450 msec) And > 10% Increase	New onset (> 450 msec) and > 10% increase in QTc means a subject who attains a value > 450 msec and > 10% increase during treatment period but not at baseline	
	New Onset (> 500 msec)	New onset (> 500 msec) in QTc means a subject who attains a value > 500 msec during treatment period but not at baseline.	
	Increase 30 - 60 msec	ase 30 - 60 msec Increase from baseline value $>$ 30 and \le 60 msec in QTc	
	Increase > 60 msec	Increase from baseline value > 60 msec in QTc	

^{*} QTc categorical change criteria apply to QTcF and QTcN.

Summary statistics of changes in ECG parameters will be provided by treatment group and scheduled visit. If ECG assessments are repeated for the same trial visit, the last repeated values will be used for generation of mean change from baseline. This is accomplished by sorting subject data by visit date and visit time (if applicable) within the same trial visit.

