Appendix 3 Criteria for Identifying ECG Measurements of Potential Clinical Relevance

Variable	Criterion Value ^a	Change Relative to Baseline ^a
Rate		
Tachycardia	≥ 120 bpm	increase of ≥ 15 bpm
Bradycardia	≤ 50 bpm	decrease of ≥ 15 bpm
Rhythm		
Sinus tachycardia ^b	≥ 120 bpm	increase of ≥ 15 bpm
Sinus bradycardia ^c	≤ 50 bpm	decrease of ≥ 15 bpm
Supraventricular premature beat	all	not present → present
Ventricular premature beat	all	not present → present
Supraventricular tachycardia	all	not present \rightarrow present
Ventricular tachycardia	all	not present \rightarrow present
Atrial fibrillation	all	not present \rightarrow present
Atrial flutter	all	not present \rightarrow present
Conduction		
1° atrioventricular block	$PR \ge 200 \text{ msec}$	increase of ≥ 50 msec
2° atrioventricular block	all	not present \rightarrow present
3° atrioventricular block	all	not present \rightarrow present
Left bundle-branch block	all	not present \rightarrow present
Right bundle-branch block	all	not present \rightarrow present
Pre-excitation syndrome	all	not present \rightarrow present
Other intraventricular conduction block ^d	QRS \geq 120 msec	increase of ≥ 20 msec
Infarction		
Acute or subacute	all	not present \rightarrow present
Old	all	not present \rightarrow present
~~~		≥ 12 weeks post study entry
ST/T Morphological		_
Myocardial Ischemia	all	not present → present
Symmetrical T-wave inversion	all	not present $\rightarrow$ present
Increase in QTc	QTcF > 450  msec	
	(male) QTcF > 470 msec	
	(female)	

^a In order to be identified as potentially clinically relevant, an on-treatment value must meet the "Criterion Value" and also represent a change from the subject's baseline value of at least the magnitude shown in the "Change Relative to Baseline" column.

^b No current diagnosis of supraventricular tachycardia, ventricular tachycardia, atrial fibrillation, atrial flutter, or other rhythm abnormality.

^c No current diagnosis of atrial fibrillation, atrial flutter, or other rhythm abnormality.

[figure not shown]
^d No current diagnosis of left bundle branch block or right bundle branch block.

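### SAP Appendix 3 flags a new old-infarction ECG only from 12 weeks after study entry, but the last scheduled ECG is at Week 8, so this one line will be empty or nearly so by construction

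*SAP*

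**What the plan says.** SAP 9.6 makes Appendix 3 the rule for the ECG safety tables: "Criteria for identifying ECG measurements of potential clinical relevance are provided in Appendix 3". Findings that meet it are listed in CT-12.2 and counted in CT-12.3.

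Footnote a of the appendix, which begins "In order to be identified as potentially clinically relevant, an on-treatment value must meet the", goes on to require both columns: the criterion value and the stated change from baseline. For an old infarction the criterion column accepts any occurrence. The change column requires the finding to be absent at baseline and present later, and adds "≥ 12 weeks post study entry". No other row of the appendix has a time condition.

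SAP 3.1 gives the length of the trial after baseline: "an 8-week (56-day) double-blind treatment period, and a 7-day safety follow-up period". Protocol Table 1.3-1 schedules 12-lead ECGs at screening, baseline, Week 4 and Week 8/ET, and marks the follow-up visit as a telephone visit. Protocol 5.4 also allows a longer screening period, with no stated limit: "additional extension of screening may be requested and discussed with the medical monitor".

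**The concern.** A 12-week threshold does not fit a trial whose last on-treatment ECG is due at 8 weeks. Suppose a subject has no infarct pattern at baseline and the Week 4 or Week 8 tracing is read centrally as an old infarction. The change from baseline is what the row was written to catch, yet the time condition would normally keep it out of the listing and the incidence table. A reader of CT-12.3 would take the zero in that line as an observed absence, when the rule had excluded the finding.

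The condition may have been carried over from a longer trial. SAP 9.2 and table CT-8.1.2 refer to a single-blind placebo run-in that this trial does not have, and SAP Appendix 2 sets LDL and HDL criteria although the laboratory list in Protocol 10.2 has only total cholesterol and triglycerides. This origin is an inference, and the point does not depend on it.

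**Working it through.** **Inputs**
- Threshold: 12 × 7 = 84 days after study entry (SAP Appendix 3).
- ECG visits: Week 4 (Day 28 ± 2, so Day 26 to 30) and Week 8/ET (Day 56 ± 2, so Day 54 to 58) (Protocol Table 1.3-1).
- Screening: from Day −28, with at least two weeks of diary, so consent by about Day −15 (Protocol 1.1 and 4.1).
- Randomization on Day −1 and first dose on Day 1 (Protocol Table 1.3-1).
- Day numbering: the protocol schedule has no Day 0, whereas the note to SAP Table 5.2-1 has one. Both are used below. They differ by one day for any interval that crosses zero.

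**The plan's own duration.** The Protocol Synopsis states: "The anticipated duration for each participant to complete the trial is up to 13 weeks". Check: 28 + 56 + 7 = 91 days, and 91 / 7 = 13.0 weeks (13.3 with the +2-day follow-up window). This reproduces the stated figure. The last week of it is the telephone follow-up, so no scheduled ECG falls there.

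**Elapsed days = ECG day − entry day, less 1 if the interval crosses zero and there is no Day 0.**

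| Study entry taken as | ECG day | No Day 0 | With Day 0 | Reaches 84? |
|---|---|---|---|---|
| First dose, Day 1 | 58 | 57 | 57 | No |
| Randomization, Day −1 | 58 | 58 | 59 | No |
| Consent, Day −15 | 58 | 72 | 73 | No |
| Consent, Day −28 | 30 (late Week 4) | 57 | 58 | No |
| Consent, Day −28 | 54 | 81 | 82 | No |
| Consent, Day −28 | 56 | 83 | 84 | Only with a Day 0 |
| Consent, Day −28 | 57 | 84 | 85 | Yes |
| Consent, Day −28 | 58 | 85 | 86 | Yes |

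From first dose or randomization the row is out of reach (57 to 59 days, or 8.1 to 8.4 weeks). From consent, a Week 4 ECG never qualifies within the 28-day screening; it would need a screening extension of at least 84 − 58 = 26 days. Early-termination ECGs fall sooner than Week 8.

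**Share of Week 8 ECGs that could qualify, if study entry means consent.** The documents give no distribution of screening length, so two assumptions are shown, both without any screening extension.
- Consent spread evenly over Day −28 to −15 (14 days) and visits evenly over Day 54 to 58 (5 days) gives 14 × 5 = 70 combinations. Without a Day 0, three reach 84 days (Day −28 with 57 or 58; Day −27 with 58): 3/70 = 4%. With a Day 0, six do (Day −28 with 56, 57 or 58; Day −27 with 57 or 58; Day −26 with 58): 6/70 = 9%.
- Every subject consents on Day −28: 2 of the 5 visit days qualify without a Day 0 (40%), and 3 of 5 with one (60%).

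**After the fix.** Without the time condition, both scheduled on-treatment ECGs qualify, as they do for the other rows defined by a change from absent to present.

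**The case against.** The strongest reply has three parts.

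*The row is not dead.* This stands in part. If study entry means consent, a subject screened for the full 28 days with an in-window ECG on Day 57 or 58 meets the threshold under either day numbering, and a longer screening makes it easier. A reader might infer that the rule fails for every on-schedule subject. The documents do not support that, because Days 57 and 58 are within the Week 8 window.

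*Little is lost.* This also stands. A reader might infer that CT-12.2 and CT-12.3 would be empty, or that such an infarction would go unrecorded in the trial. Neither follows. The tables cover every row of Appendix 3, and only one line is affected. Acute or subacute infarction, myocardial ischemia and symmetrical T-wave inversion carry no time limit. Under Protocol 8.7.4, ECGs are also evaluated at the site, and an abnormality that the investigator judges clinically significant is recorded as an adverse event. That route depends on the investigator's judgment, however, whereas Appendix 3 is there to give a count by fixed criteria.

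*The delay may be deliberate,* to avoid counting an infarct that predates the trial. The SAP does not say so. The row already requires absence at baseline, screening ECGs are taken in triplicate, and one central service reads all ECGs. If the filter is intended, it still leaves a row that can hardly operate in this trial, with an undefined starting point.

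**Conclusion.** The point holds as a minor one. The time condition on the old-infarction row does not fit the ECG schedule. If study entry is randomization or first dose, the row cannot fire. If it is consent, Week 4 ECGs are excluded and only a late corner of the Week 8 ECGs qualifies: 4% to 9% under an even spread of consent and visit days, and 40% to 60% in the extreme case where every subject consents on Day −28. With few events expected among about 126 subjects, that line will be empty or nearly so by construction.

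This rests on the scheduled visits and their stated windows. A longer screening raises the consent-based shares by an amount the documents do not allow one to calculate. An unscheduled ECG would have to be on treatment and equally late to qualify.

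No efficacy endpoint, test or error rate is affected. Nor should the point be read as implying a known infarction signal: the protocol's only adverse event of special interest is skin eruption, and Protocol 2.3 anticipates no risks particular to this population.

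**What to change.** In SAP Appendix 3, delete the 12-week condition from the old-infarction row, so that any change from absent at baseline to present on an on-treatment ECG is listed and counted. Keep the row separate from the acute or subacute row, so that the two readings are not merged.

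The cost is one edit, best made before unblinding. The downside is that an old pattern overlooked on the baseline ECG may occasionally be listed as a change, but it can be recognized and judged from the listing. If the sponsor wants to keep a time filter, the SAP should define study entry, give the reason for the filter, and note in CT-12.3 that the row can seldom or never be met on this schedule.

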#### **Appendix 4** List of Proposed Summary Tables

- CT-1.1 Subject Disposition
- CT-1.2 Subject Disposition by Center
- CT-1.3 Subject Completion Rates by Week (Randomized Analysis Set)
- CT-2 Reasons for Discontinuation (Randomized Analysis Set)
- CT-3.1 Demographic Characteristics (Randomized Analysis Set)
- CT-3.2.1 Medical History (Randomized Analysis Set)
- CT-3.2.2 Psychiatric History (Randomized Analysis Set)
- CT-3.3 Baseline Disease Evaluations (Randomized Analysis Set)
- CT-4.1 Concomitant Medications: Medications Taken Prior to Start of Study Period (Randomized Analysis Set)
- CT-4.2 Concomitant Medications: Medications Taken During the Study Period (Randomized Analysis Set)
- CT-4.3 Concomitant Medications: Medications Taken Post Study Period (Randomized Analysis Set)

CCL

CT-5.2.1 Summary of Change from Baseline in Binge Eating Days per Week - MMRM (Efficacy Analysis Set)

CT-5.3.1 Summary of Change from Baseline in Clinical Global Impression - Severity Score - MMRM (Efficacy Analysis Set)

CCI

- CCI
- CT-5.3.5 Summary of Change from Baseline in Clinical Global Impression Severity Score ANCOVA (Efficacy Analysis Set)
- CT-5.4.1 Summary of Clinical Global Impression Change Score LOCF (Efficacy Analysis Set)
- CT-5.4.2 Summary of Clinical Global Impression Change Score OC (Efficacy Analysis Set)
- CT-5.5.1.1 Summary of Change from Baseline in Yale-Brown Obsessive-Compulsive Scale Modified for Binge Eating Total Score MMRM (Efficacy Analysis Set)
- CT-5.5.1.2 Summary of Change from Baseline in Yale-Brown Obsessive-Compulsive Scale Modified for Binge Eating Total Score ANCOVA (Efficacy Analysis Set)
- CT-5.5.2.1 Summary of Change from Baseline in Yale-Brown Obsessive-Compulsive Scale Modified for Binge Eating Obsession Score MMRM (Efficacy Analysis Set)
- CT-5.5.2.2 Summary of Change from Baseline in Yale-Brown Obsessive-Compulsive Scale Modified for Binge Eating Obsession Score ANCOVA (Efficacy Analysis Set)
- CT-5.5.3.1 Summary of Change from Baseline in Yale-Brown Obsessive-Compulsive Scale Modified for Binge Eating Compulsion Score MMRM (Efficacy Analysis Set)
- CT-5.5.3.2 Summary of Change from Baseline in Yale-Brown Obsessive-Compulsive Scale Modified for Binge Eating Compulsion Score ANCOVA (Efficacy Analysis Set)
- CT-5.5.4 Categorical Analysis of Yale-Brown Obsessive-Compulsive Scale Modified for Binge Eating (Efficacy Analysis Set)
- CT-5.6.1 Summary of Change from Baseline in Number of Binge Episodes per Week MMRM (Efficacy Analysis Set)
- CT-5.6.2 Summary of Change from Baseline in Number of Binge Episodes per Week MMRM (Efficacy Analysis Set)
- CT-5.7 Proportion of Subjects with 4-week Cessation from Binge at Week 8/ET (Efficacy Analysis Set)
- CT-5.8.1 Summary of Change from Baseline in Patient Global Impression Severity Score MMRM (Efficacy Analysis Set)
- CT-5.8.2 Summary of Change from Baseline in Patient Global Impression Severity Score ANCOVA (Efficacy Analysis Set)
- CT-5.9.1 Summary of Patient Global Impression Change Score LOCF (Efficacy Analysis Set)
- CT-5.9.2 Summary of Patient Global Impression Improvement Change Score OC (Efficacy Analysis Set)
- CT-5.10.1.1 Summary of Change from Baseline in 36-item Short-form Health Survey Version 2 (SF-36v2) Physical Component Summary Score MMRM (Efficacy Analysis Set)
- CT-5.10.1.2Summary of Change from Baseline in 36-item Short-form Health Survey Version 2 (SF-36v2) Physical Component Summary Score ANCOVA (Efficacy Analysis Set)

- CT-5.10.2.1 Summary of Change from Baseline in 36-item Short-form Health Survey Version 2 (SF-36v2) Mental Component Summary Score MMRM (Efficacy Analysis Set)
- CT-5.10.2.2 Summary of Change from Baseline in 36-item Short-form Health Survey Version 2 (SF-36v2) Mental Component Summary Score ANCOVA (Efficacy Analysis Set)
- CT-5.11.1 Eating Disorder Examination Questionnaire 7-Item Version (EDE-Q7) Global Score ANCOVA (Efficacy Analysis Set)
- CT-5.11.2 Eating Disorder Examination Questionnaire 7-Item Version (EDE-Q7) Dietary Restraint Subscale Score ANCOVA (Efficacy Analysis Set)
- CT-5.11.3 Eating Disorder Examination Questionnaire 7-Item Version (EDE-Q7)
- Shape/Weight Overvaluation Subscale Score ANCOVA (Efficacy Analysis Set)
- CT-5.11.4 Eating Disorder Examination Questionnaire 7-Item Version (EDE-Q7) Body Dissatisfaction Subscale Score ANCOVA (Efficacy Analysis Set)
- CT-6.1.1 Columbia-Suicide Severity Rating Scale Suicidality (Safety Analysis Set)
- CT-6.1.2 Columbia-Suicide Severity Rating Scale Suicidal Behavior by Type (Safety Analysis Set)
- CT-6.1.3 Columbia-Suicide Severity Rating Scale Suicidal Ideation by Type (Safety Analysis Set)
- CT-6.1.4 Columbia-Suicide Severity Rating Scale Treatment Emergent Suicidal Behavior and Ideation (Safety Analysis Set)
- CT-6.1.5 Columbia-Suicide Severity Rating Scale Listing of Treatment Emergent Suicidal Behavior (Safety Analysis Set)
- CT-6.1.6 Columbia-Suicide Severity Rating Scale Listing of Treatment Emergent Suicidal Ideation (Safety Analysis Set)
- CT-6.1.7 Columbia-Suicide Severity Rating Scale Listing of Treatment Emergent Serious Suicidal Ideation (Safety Analysis Set)
- CT-6.1.8 Columbia-Suicide Severity Rating Scale Listing of Worsening Suicidal Ideation (Safety Analysis Set)
- CT-6.2 Summary of Change from Baseline in Hamilton Anxiety Rating Scale Total Score (Safety Analysis Set)
- CT-6.3 Summary of Change from Baseline in Montgomery-Asberg Depression Rating Scale Total Score (Safety Analysis Set)
- CT-6.4 Summary of Study Medication Withdrawal Questionnaire (SMWQ) Total Score (Safety Analysis Set)
- CT-7.1 Extent of Exposure (Safety Analysis Set)
- CT-7.2 Number and Percentage of Subjects Receiving Study Medication and Mean and Range of Average Daily Dose (Safety Analysis Set)
- CT-8.1.1 Adverse Events (All Causalities) (Safety Analysis Set)
- CT-8.1.2 Adverse Events During the Single-Blind Placebo Run-in Period (All Causalities) (Safety Analysis Set)
- CT-8.2.1 Incidence of Treatment-Emergent Adverse Events by System Organ Class and MedDRA Preferred Term (Safety Analysis Set)
- CT-8.2.2 Incidence of Treatment-Emergent Adverse Events by System Organ Class, MedDRA Preferred Term and Severity (Safety Analysis Set)

- CT-8.2.3 Incidence of Treatment-Emergent Adverse Events of at Least 5% in Any Centanafadine Group and Greater Than Placebo by System Organ Class and MedDRA Preferred Term (Safety Analysis Set)
- CT-8.2.4 Incidence of Non-Serious Treatment-Emergent Adverse Events of at Least 5% in Any Centanafadine Group and Greater Than Placebo by System Organ Class and MedDRA Preferred Term (Safety Analysis Set)
- CT-8.2.5 Incidence of TREATMENT-EMERGENT ADVERSE Events of at Least 2% in Any Centanafadine Group and Greater Than Placebo by System Organ Class and MedDRA Preferred Term (Safety Analysis Set)
- CT-8.2.6 Incidence and Occurrence (Number of Events) of Serious Treatment-Emergent Adverse Events by System Organ Class and MedDRA Preferred Term (Safety Analysis Set)
- CT-8.2.7 Incidence and Occurrence (Number of Events) of Potentially Drug-Related Serious Treatment-Emergent Adverse Events by System Organ Class and MedDRA Preferred Term (Safety Analysis Set)
- CT-8.2.8 Incidence and Occurrence (Number of Events) of Non-Serious Treatment-Emergent Adverse Events by System Organ Class and MedDRA Preferred Term (Safety Analysis Set)
- CT-8.3.1 Incidence of Potentially Drug-Related Treatment-Emergent Adverse Events by System Organ Class and MedDRA Preferred Term (Safety Analysis Set)
- CT-8.3.2 Incidence of Potentially Drug-Related Treatment-Emergent Adverse Events by System Organ Class, MedDRA Preferred Term and Severity (Safety Analysis Set)
- CT-8.4.1 Incidence of Deaths Due to Treatment-Emergent Adverse Events by System Organ Class and MedDRA Preferred Term (Safety Analysis Set)
- CT-8.4.2 Incidence of Deaths Due to Treatment-Emergent Adverse Events by System Organ Class and MedDRA Preferred Term and Severity (Safety Analysis Set)
- CT-8.5.1 Incidence of Serious Treatment-Emergent Adverse Events by System Organ Class and MedDRA Preferred Term (Safety Analysis Set)
- CT-8.5. 2 Incidence of Serious Treatment-Emergent Adverse Events by System Organ Class, MedDRA Preferred Term and Severity (Safety Analysis Set)
- CT-8.6.1 Incidence of Treatment-Emergent Adverse Events Resulting in Discontinuation of Investigational Medicinal Product by System Organ Class and MedDRA Preferred Term (Safety Analysis Set)
- CT-8.6.2 Incidence of Treatment-Emergent Adverse Events Resulting in Discontinuation of Investigational Medicinal Product by System Organ Class, MedDRA Preferred Term and Severity (Safety Analysis Set)
- CT-8.7.1 Incidence of Treatment-Emergent Adverse Events of Special Interests related to Rash by System Organ Class and MedDRA Preferred Term (Safety Analysis Set)
- CT-8.7.2 Incidence of Treatment-Emergent Adverse Events of Special Interests related to Rash by System Organ Class and MedDRA Preferred Term and Severity (Safety Analysis Set)
- CT-8.8.1 Incidence of Treatment-Emergent Adverse Events related to Abuse by System Organ Class and MedDRA Preferred Term (Safety Analysis Set)
- CT-8.8.2 Incidence of Treatment-Emergent Adverse Events related to Abuse by System Organ Class and MedDRA Preferred Term and Severity (Safety Analysis Set)

- CT-8.9.1 Incidence of Treatment-Emergent Adverse Events involving Medication Handling Irregularities by System Organ Class and MedDRA Preferred Term (Safety Analysis Set)
- CT-8.9.2 Incidence of Treatment-Emergent Adverse Events involving Medication Handling Irregularities by System Organ Class and MedDRA Preferred Term and Severity (Safety Analysis Set)
- CT-9.1 Listing of Deaths
- CT-9.2 Listing of Serious Adverse Events
- CT-9.3 Listing of Adverse Event Leading Discontinuations of Investigation Medicinal Products
- CT-9.4 Listing of Treatment-Emergent Adverse Events of Special Interests related to Rash
- CT-9.5 Listing of Treatment-Emergent Adverse Events related to Abuse
- CT-9.6 Listing of Treatment-Emergent Adverse Events involving Medication Handling Irregularities
- CT-10.1 Criteria for Laboratory Test Values with Potential Clinical Relevance
- CT-10.2.1 Listing of Laboratory Test Values with Potential Clinical Relevance by Subject (Safety Analysis Set)
- CT-10.2.2 Listing of Laboratory Test Values with Potential Clinical Relevance by Test (Safety Analysis Set)
- CT-10.3 Incidence of Laboratory Test Values with Potential Clinical Relevance (Safety Analysis Set)
- CT-10.4.1.1 Summary of Change from Baseline in Clinical Laboratory Test Results Serum Chemistry (Safety Analysis Set)
- CT-10.4.1.2 Summary of Change from Baseline in Clinical Laboratory Test Results Lipid Parameters ANCOVA (Safety Analysis Set)
- CT-10.4.2 Summary of Change from Baseline in Clinical Laboratory Test Results Hematology (Safety Analysis Set)
- CT-10.4.3 Summary of Change from Baseline in Clinical Laboratory Test Results Urinalysis (Safety Analysis Set)
- CT-10.5.1 Incidence of Potentially Liver Injury Related Laboratory Test Abnormalities (Safety Analysis Set)
- CT-10.5.2 Listing of Potentially Liver Injury Related Laboratory Test Abnormalities (Safety Analysis Set)
- CT-11.1 Criteria for Potentially Clinically Relevant Abnormalities in Vital Signs
- CT-11.2 Listing of Potentially Clinically Relevant Abnormalities in Vital Signs (Safety Analysis Set)
- CT-11.3 Incidence of Potentially Clinically Relevant Abnormalities in Vital Signs (Safety Analysis Set)
- CT-11.4 Summary of Change from Baseline in Vital Signs (Safety Analysis Set)
- CT-12.1 Criteria for Potentially Clinically Relevant Abnormalities in ECG Evaluations
- CT-12.2 Listing of Potentially Clinically Relevant Abnormalities in ECG Evaluations (Safety Analysis Set)
- CT-12.3 Incidence of Potentially Clinically Relevant Changes in ECG Evaluations (Safety Analysis Set)
- CT-12.4 Mean Change from Baseline in Electrocardiogram Results (Safety Analysis Set)

- CT-12.5 Incidence of Categorical Changes in QT/QTc (Safety Analysis Set)
- CT-13.1.1 Summary of Change from Baseline in Body Weight by Mapped Week MMRM (Safety Analysis Set)
- CT-13.1.2 Summary of Change from Baseline in Body Weight by Mapped Week ANCOVA (Safety Analysis Set)
- CT-13.2.1 Summary of Percentage of Change from Baseline in Body Weight by Mapped Week MMRM (Safety Analysis Set)
- CT-13.2.2 Summary of Percentage of Change from Baseline in Body Weight by Mapped Week ANCOVA (Safety Analysis Set)
- CT-13.3 Summary of Proportion of Subjects with Potentially Clinically Relevant Weight Gain or Weight Loss by Mapped Week (Safety Analysis Set)
- CT-13.4.1 Summary of Change from Baseline in BMI by Mapped Week (Safety Analysis Set)
- CT-13.4.2 Classification of BMI by Mapped Week (Safety Analysis Set)
- CT-14 Summary of Medication Handling Irregularity (Safety Analysis Set)
- CT-15 Summary of Events Reported as Findings in Events Subject to Additional Monitoring (Safety Analysis Set)

